18.2 Demographic and Baseline Characteristics

The following demographic variables at screening will be summarized by treatment group and study part. While the study is too small to expect statistical significance in sub-groups, the efficacy and safety results will be examined by standard age categories (neonates (0-to-1 month of age), infants and toddlers (1 month to 2 years of age) and children (>2 years of age)) and any clinically important differences reported.

18.3 Definition of Numeric Efficacy Outcomes

Subjective Image Quality Scores: The image quality will be independently scored by 2 board certified blinded readers with >5 years of cardiovascular MRI reading experience using a 1-4 point scale (1). The composite image quality score for each subject will be a number between 7 (all subjective image quality scores are 1=non-diagnostic) to 28 (all subjective image quality scores are 4=clear visualization). The scores will be assessed separately for each of the following seven anatomical structures that are important for imaging pediatric CHD patients: the aortic root, the pulmonary artery (PA), the coronary arteries, the out-flow tracts, the valves, the ventricles, and the atria. If the difference in the composite score is greater than or equal to 4 between two image readers, the readers will read the image together in a consensus reading session and arrive at a consensus for each of the 7 structures. The criteria for assigning scores will be as follows: 1) For **aortic root and PA**, 1=nondiagnostic (vessels not visualized or diagnostically not assessable due to small size and /or motion artifact and /or poor contrast enhancement), 2=vessels visualized but with poor contrast enhancement and /or motion artifact so as to limit confident assessment and measurement of dimensions, 3=vessels visualized with good contrast so as to enable confident assessment of patency but with poor edge definition due to motion artifact so as to limit confident measurement of dimensions, 4=vessels visualized with good contrast and good edge definition such that patency and dimensions are confidently assessable; 2) For **coronary arteries**: 1=nondiagnostic (vessels not visualized or diagnostically not assessable due to small size and /or motion artifact and /or poor contrast enhancement), 2=only origins of main coronary arteries confidently identifiable, 3=origins and proximal course of RCA and left anterior descending (LAD) confidently evaluable, 4=origin, proximal and mid courses of RCA and LAD and proximal takeoff of left circumflex confidently evaluable; 3) For **out-flow tracts and valves**: 1=nondiagnostic (structures not visualized or diagnostically not assessable due to small size and /or motion artifact and /or poor contrast enhancement, 2=annulus and sinotubular junction visualized but borders not sufficiently well defined for confident measurement, 3=annulus and sinotubular junction visualized with well defined borders sufficient for confident measurement, 4=annulus and sinotubular junction clearly visualized with well defined borders sufficient for confident measurement and valve leaflets clearly seen; 4) For the **ventricles and atria**: 1=nondiagnostic (chambers not visualized or diagnostically not assessable due to small size and /or motion artifact and /or poor contrast enhancement, 2=chambers distinguishable but walls poorly defined and only gross features evaluable, 3=chambers clearly distinguishable with well defined septum and free walls confidently evaluable but with poor definition of the papillary

muscles and trabeculae, 4=chambers clearly distinguishable with excellent wall definition and with clear definition of the papillary muscles and trabeculae.

Image Sharpness Values: Objective image sharpness will be measured through the interventricular septum and ascending aorta using a previously described method (1). The image sharpness scores will be measured by drawing a linear signal profile and calculating the slope of the signal intensity curve. The slope is defined as the image intensity difference divided by the distance between the two points at 20% and 80% of the dynamic range, respectively.

Blood-Myocardium CNR: The blood-myocardium CNR will be measured by drawing three regions of interest (ROI), one at the center of left ventricular (LV) cavity, one at the interventricular septum and one in the background air region. The CNR will be calculated as the difference in mean signal intensity between the LV cavity ROI and the septum ROI divided by the standard deviation of the background air ROI signal.

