7.3 Study Design Part II: diagnostic efficacy of ventilator-gated MUSIC-MRI vs. self-gated MUSIC-MRI

The Part II study will commence after statistical significance of the primary endpoint of Part I is confirmed. The overall goal of Part II is to develop and validate a more advanced MUSIC-MRI pulse sequence that incorporates image acceleration and compressed sensing reconstruction techniques as well as respiratory motion self-gating methods. Our current MUSIC-MRI pulse sequence is designed for young patients (newborn to 6 years old) who undergo cardiovascular MRI under general anesthesia or sedation per our institutional standard practice. The ventilator air pressure signal is currently used as a respiratory motion gating signal in our ventilator-gated MUSIC-MRI pulse sequence. For older children with CHD who can reliably follow verbal instructions during the MRI examination, undergoing sedation or anesthesia for the purpose of MRI would not be justifiable. Therefore, a free-breathing self-gated MUSIC-MRI pulse sequence

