12.2 MRI Procedures

12.2.1 Patient Preparation and Setup

All patients will undergo MRI on an FDA approved, clinical 18-channel Siemens 3.0T Magnetom TIM Trio scanner, and running version B17 software. The appropriate RF receiver coil configuration will be chosen depending on patient size; for example neonates may be studied using a 16 element adult knee coil, infants using an adult head-neck coil combination and older children using surface flex coils or a body array coil. Fixed (spine) coil elements in the patient table may be used in combination with any of the other coils (except the knee coil).

Prior to Feraheme or Ablavar infusion, all patients will be asleep, intubated and ventilated such that, in the case of a clinically urgent or life-threatening AE, there will already be in place full

airway protection, physiological monitoring and support of respiration. Consistent with institutional clinical practice at UCLA, anesthesia in the pediatric CHD patients will be performed by specialized pediatric anesthesiologists regardless of contrast agent used (Feraheme vs. Ablavar) with continuous monitoring of heart rate, blood pressure, pulse oximetry, end tidal CO₂, and, where appropriate, anesthetic gas levels (such as sevoflurane). In the case of a SAE, changes in vital signs will be recognized immediately and appropriate treatment initiated. All of the children in our study will have protected airways and mechanical ventilatory support from the start of the procedure to the end. Serious adverse reactions to any agent may include laryngeal edema and bronchospasm, where prior endotracheal intubation may be lifesaving. Should other events occur involving changes in heart rate, heart rhythm and /or blood pressure, the anesthesiologist can focus his / her attention on the appropriate use of chronotropic or inotropic agents, intravenous fluids and /or vasoactive drugs, without having to secure the airway. All patient physiological monitoring data are, and will continue to be, digitized and transferred in real time to the electronic patient medical record, where they are stored permanently and retrievably. Relevant abstractions from these and other patient safety data (protected health information removed) will be included in our DMC, IRB and IND adverse event reports.

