12.2.3 MRI Scanning Procedures

As for all patients, the MRI system will perform automatic adjustment procedures to optimize the homogeneity of the magnetic field, customized to the individual patient. It will also perform standard RF frequency adjustment of the transmitter RF field and calibration of the receiver coil elements. All parameters for RF dose (SAR or specific absorption rate) and gradient switching rates will be within FDA approved limits and monitored continuously by permanent and immutable software and hardware watchdogs (Siemens product specifications on file at FDA).

With the patient being ventilated continuously, the following MRI pulse sequences will be performed:

For Study Part I, each patient (regardless of test or control group assignment) will undergo MRI using the following MRI pulse sequences: 1) Conventional 2D cine imaging for cardiac function assessment and phase-contrast MRI for flow quantification in imaging planes specified by a radiologist or cardiologist at the point of delivery, per our institutional standard practice regardless of our research protocol. These image acquisitions are necessary to ensure that each patient will get a diagnostic MRI study regardless the outcome of our research and will only be performed when the patient is considered by the supervising anesthesiologist to be stable for ventilator-controlled breath-hold maneuvers; 2) The 3D cine ventilator-gated MUSIC-MRI MRI, based on which the Feraheme vs. Ablavar comparison will be performed.

For Study Part II, each patient will undergo the same MRI pulse sequence as Part I of our study. In addition, each patient will undergo the to-be-developed self-gated MUSIC-MRI MRI and the order of the ventilator-gated MUSIC-MRI and the self-gated MUSIC-MRI will be randomized. The self-gated MUSIC-MRI pulse sequence will require an additional 5 min of scan time and anesthesia time without breath holding, which the investigators feel does not add significant additional risk to the patient.

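### Sharpness in Section 18.3 is an unnormalised intensity slope, so it scales with edge contrast and image gain as well as with edge width

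*Combined protocol and SAP*

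**What the plan says.** All references are to the combined protocol and SAP.

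- **Definition (Section 18.3, Image Sharpness Values).** Sharpness is obtained by "drawing a linear signal profile and calculating the slope of the signal intensity curve". The formula follows: "The slope is defined as the image intensity difference divided by the distance between the two points at 20% and 80" per cent of the profile's dynamic range. The paragraph cites the earlier feasibility study (reference 1) as the source of the method. It states no division by the range, the signal level or the noise.
- **CNR (next paragraph of 18.3).** The blood-septum signal difference is "divided by the standard deviation of the background air ROI signal".
- **Acquisition.** All patients use one scanner model, but Section 12.2.1 says: "The appropriate RF receiver coil configuration will be chosen depending on patient size". Section 12.2.3 adds a per-patient "standard RF frequency adjustment of the transmitter RF field and calibration of the receiver coil elements". No common intensity scale is stated.
- **Part I use.** Sharpness at the septum and at the ascending aorta are two of the ten secondary endpoints in the Synopsis. Section 18.5.1 compares them between different children with a two-group t-test. The Synopsis rationale expects weaker blood-tissue contrast with Ablavar.
- **Part II use.** Section 8.2.2 lists non-inferior sharpness as a secondary endpoint, and Section 18.5.2 uses a paired t-test. Section 7.3 describes a self-gated sequence that "incorporates image acceleration and compressed sensing reconstruction techniques". Both sequences are run in the same child in one session.

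**The concern.** A sharpness measure should respond to how abruptly the signal changes across a boundary. The 18.3 formula also responds to how large the change is. The plan elsewhere treats these as different things: on its reader scale for the aortic root and pulmonary artery, score 3 is good contrast with poor edge definition, and score 4 requires both. The objective measure cannot separate the two.

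At stake is the reading of two secondary endpoints. In Part I an expected contrast difference between agents could appear as a sharpness difference although edge widths are equal, and so count partly a second time beside CNR. This could affect a decision. If the Part I primary comparison is not significant, Section 7.3 asks the DMC to weigh superiority on the secondary endpoints when it advises on the agent for Part II. In Part II, a difference in image scaling between the two reconstructions, if there is one, would enter the paired comparison directly.

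**Working it through.** The documents state no sharpness mean, SD, effect or margin, so there is no plan figure to reproduce. The check is algebraic, with a numerical illustration.

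**Step 1: the formula.** Let R be the dynamic range of the profile (maximum minus minimum) and d the distance between its 20% and 80% points.

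Slope = (0.8R − 0.2R) / d = 0.6R / d.

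The 20% and 80% rule makes d independent of R for a given edge shape. It does not remove R from the numerator.

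- Multiply the image by a gain g: R becomes gR, d is unchanged, and the slope is multiplied by g.
- Add a uniform offset: R and d are unchanged, and so is the slope.
- Divide by R: 0.6 / d, which depends on edge width only.

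**Step 2: numerical check.** The edge is a step blurred by a Gaussian. The intensities (100 to 400, so R = 300) and the blur (SD 1 mm) are assumed for illustration.

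| Edge | R | d (mm) | 0.6R/d (per mm) | Ratio to base | 0.6/d (per mm) |
|---|---|---|---|---|---|
| Base, blur 1 mm | 300 | 1.683 | 106.9 | 1.00 | 0.356 |
| Offset +200 | 300 | 1.683 | 106.9 | 1.00 | 0.356 |
| Gain ×2 | 600 | 1.683 | 213.9 | 2.00 | 0.356 |
| Contrast ×1.5 | 450 | 1.683 | 160.4 | 1.50 | 0.356 |
| Blur 1.5 mm | 300 | 2.525 | 71.3 | 0.67 | 0.238 |
| Contrast ×1.5, blur 1.5 mm | 450 | 2.525 | 106.9 | 1.00 | 0.238 |
| Contrast ×2, blur 1.5 mm | 600 | 2.525 | 142.6 | 1.33 | 0.238 |

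In the last two rows the edge is 50% wider than base, yet the raw slope scores it as equal to base and then as sharper. The normalised value moves only when the blur moves.

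**Step 3: comparison with CNR.** A common gain multiplies both the signal difference and the background SD, so it cancels from CNR. The sharpness formula has no such divisor.

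**Step 4: what this could do to the Part I test.** The assumptions, none of them from the documents except the group size of 40 (Section 18.7.1), are lognormal sharpness values with between-child CV of 0.3 or 0.5, identical edge widths in the two groups, two-sided 0.05 (no level is stated for sharpness), and 20,000 simulated trials.

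| Contrast difference between agents | Chance of a significant sharpness result (CV 0.5 to CV 0.3) |
|---|---|
| None | about 5% |
| 10% | 13% to 28% |
| 25% | 50% to 91% |
| 50% | 95% to 100% |

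With 36 per group the last three rows become 12% to 26%, 47% to 88%, and 93% to 100%.

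**Step 5: Part II.** Child, coil and session are shared within a pair, so they largely cancel. If the self-gated reconstruction were scaled by a factor g relative to the ventilator-gated one, its slope would be multiplied by g at unchanged edge width. The documents give no value for g and do not say that it differs from 1.

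**The case against.** The strongest reply is that Section 18.3 cites a previously described method, and that method may normalise the profile or fix the intensity scale. The cited paper is not part of the documents, so this cannot be excluded. It does not settle the matter, because 18.3 writes out a formula without that step. Either the formula is the method, or 18.3 leaves out part of it; one added sentence is needed in both cases.

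A second reply is that an absolute gradient may be intended, since enhancement is one route by which an agent improves the visible boundary. That is a legitimate construct and a reason to keep the raw slope as a supportive value. As the only sharpness measure, it leaves edge width unidentified.

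Several stronger readings are tempting but unsupported:

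- **That the measure tracks brightness in general.** A uniform offset cancels; only the step across the edge and multiplicative gain matter.
- **That coil choice distorts both Parts.** Coils follow patient size, not agent. In Part I this mainly adds between-child variance, and it biases the comparison only if size differs between groups. That is possible, because guardians choose the agent, but it is not shown. In Part II coil effects largely cancel.
- **That sharpness merely repeats CNR.** Edge width also enters the slope, and one of the two sites is the ascending aorta, whereas CNR uses the LV cavity and septum. The overlap is partial.
- **That the two Part II reconstructions differ in intensity scale.** They may; nothing in the documents says that they do.

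**Conclusion.** The concern holds for the formula as written. The sharpness endpoint equals 0.6 × range / distance, so it is proportional to edge contrast and to gain as well as to the inverse of edge width. The proportionality is exact: 50% more contrast at the same width gives a 50% higher value. It rests on taking the 18.3 formula at its word, subject to what the cited method may add.

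In Part I a sharpness difference could arise with no difference in edge width. The 50% to 91% chance of significance at a 25% contrast difference shows scale only, because both the CVs and the contrast difference are assumed. In Part II the exposure is conditional on a scaling difference between reconstructions. A reader might infer that the trial's main conclusion is at risk; it is not. Sharpness is secondary in a study described as exploratory, and the primary endpoint, the sample size and the interim rule do not use it. The change should be made, but the plan does not fail without it.

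**What to change.** In Section 18.3, for both Parts, state that each profile is scaled to its own dynamic range before the slope is computed, so that sharpness = 0.6 / (20–80% distance), per mm; or report the 20–80% distance itself. Keep the raw slope as a supportive value for comparability with the cited method, and say whether that method normalises.

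The same profiles and points are used, so no further imaging or reading is needed. The small downside is that the normalised value no longer carries the contrast component, which CNR already measures, and it may differ from the previously published metric. Section 18.5.2 gives a non-inferiority margin for the image quality scores only; a value in per-mm units would also make a sharpness margin easier to define than one in arbitrary intensity units.

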18.4 Primary Efficacy Endpoints

18.4.1 Part I – Difference in the composite image quality score between Feraheme and Ablavar

The primary efficacy endpoint for Part I is the composite image quality score, which is defined as the sum of the subject image quality scores assigned to seven important anatomical structures for pediatric CHD patients: the aortic root, the PA, the coronary arteries, the outflow tracts, the valves, the ventricles, and the atria. The score will be the average scores from all the image readers. The consensus reading will occur if the difference in the composite score from the same image is 4 or greater. The composite image quality score will be tested for normality using the Shapiro-Wilk and Shapiro-Francia tests. For normally distributed data, comparison will be made between the composite image quality scores for Feraheme and Ablavar using a parametric two-sided t-test with an appropriate transformation if needed. If statistical transformation of the image quality score is not possible, a non-parametric Wilcoxon-rank-sum test can be considered. The null hypothesis is that there is no difference in the composite subjective image quality scores between Feraheme and Ablavar. This comparison will be a two-sided test at the overall 0.05 level of significance. Summary statistics of mean, standard deviation and their 95% confidence intervals of each contrast agent and the difference will be used for statistical description. There will be a formal interim analysis and a primary analysis for image quality score. The primary analysis of image quality scores will be performed when 80 CHD subjects are enrolled and the images are scored by the image readers. Scores for subjective image quality, sharpness and CNR measurements will remain blinded from the Investigators and only the study statistician will be able to pair the contrast assignment and the score.

[Interim Analyses]: To avoid performing a study with larger-than-necessary enrollment for Part I of our study, a formal interim analysis for the composite imaging score will be performed at approximately 20 CHD subjects for each of the contrast group (50% of the target number for the primary analysis). Alpha-spending for the interim analyses and the primary analysis will be 0.025 and 0.025 (both two-sided), respectively. The overall alpha for the composite image quality score will be preserved at the two-sided 0.05 significance level. The interim analysis of the composite image quality score will be conducted by an independent statistician under the charter of the DMC.

The interim effect of Feraheme compared to the Ablavar of ventilator-gated MUSIC-MRI based on the average composite score from two image readers will be tested with a two group t-test with an appropriate transformation if needed. Non-parametric Wilcoxon rank sum test will be considered if the data are not normally distributed based on the Shapiro-Wilk and Shapiro-Francia tests and transformation is not feasible.

18.4.2 Part II – Difference in the composite image quality score between ventilator-gated and self-gated MUSIC-MRI

The primary efficacy endpoint for Part II is the composite image quality score defined in 18.4.1. Data will be tested for normality using the Shapiro-Wilk and Shapiro-Francia tests. The composite subjective image quality score will be compared between ventilator-gated MUSIC-MRI and the self-gated MUSIC-MRI using a paired t-test with appropriate transformation if needed. If the data are not normally distributed and transformation is not possible, a Wilcoxon-sign-rank test will be considered. The null hypothesis is that the mean difference in the image quality scores of the self-gated images is smaller than or equal to the mean from ventilator-gated images with the non-inferiority margin of -1.75 (self-ventilator ≤ -1.75). The alternative hypothesis is that the mean difference in image quality score of self-gated images from the ventilator-gated images is greater than the non-inferiority margin of -1.75 (self-ventilator > -1.75) (see the detail of choosing the margin in section 18.7.2.).

Rejection of the null hypothesis will occur if the p-value is ≤ 0.025 . Scores for subjective image quality will remain blinded from the Investigators and only the study statistician will be able to pair the MRI pulse sequence and the score. No interim analyses will be performed in Part II of the study.

